### **7.2.3 Evaluating Adverse Events**

An investigator who is a qualified physician will evaluate all adverse events according to the NCI Common Terminology for Adverse Events (CTCAE), version 4.0. Any adverse event which changes CTCAE grade over the course of a given episode will have each change of grade recorded on the adverse event case report forms/worksheets.

All adverse events regardless of CTCAE grade must also be evaluated for seriousness.

Table 6. Evaluating Adverse Events

An investigator who is a qualified physician, will evaluate all adverse events as to:

V4.0 CTCAE Grading	Grade 1	Mild; asymptomatic or mild symptoms; clinical or diagnostic observations only; intervention not indicated.
	Grade 2	Moderate; minimal, local or noninvasive intervention indicated; limiting age-appropriate instrumental ADL.
	Grade 3	Severe or medically significant but not immediately life-threatening; hospitalization or prolongation of hospitalization indicated; disabling; limiting self-care ADL.
	Grade 4	Life threatening consequences; urgent intervention indicated.
	Grade 5	Death related to AE
Seriousness	A serious adverse event is any adverse event occurring at any dose or during any use of Merck product that:	
	† Results in death; or	
	† Is life threatening; or places the subject, in the view of the investigator, at immediate risk of death from the event as it occurred (Note: This does not include an adverse event that, had it occurred in a more severe form, might have caused death.); or	
	† Results in a persistent or significant disability/incapacity (substantial disruption of one's ability to conduct normal life functions); or	
	† Results in or prolongs an existing inpatient hospitalization (hospitalization is defined as an inpatient admission, regardless of length of stay, even if the hospitalization is a precautionary measure for continued observation. (Note: Hospitalization for an elective procedure to treat a pre-existing condition that has not worsened is not a serious adverse event. A pre-existing condition is a clinical condition that is diagnosed prior to the use of a Merck product and is documented in the patient's medical history.); or	
	† Is a congenital anomaly/birth defect (in offspring of subject taking the product regardless of time to diagnosis); or	
	Is a new cancer (that is not a condition of the study) (although not serious per ICH definition, is reportable to the Sponsor within 24 hours and to Merck within 2 working days to meet certain local requirements); or	
	Is an overdose (whether accidental or intentional). Any adverse event associated with an overdose is considered a serious adverse event for collection purposes. An overdose that is not associated with an adverse event is considered a non-serious event of clinical interest and must be reported within 24 hours to the Sponsor and to Merck within 2 working days..	

	
Other important medical events that may not result in death, not be life threatening, or not require hospitalization may be considered a serious adverse event when, based upon appropriate medical judgment, the event may jeopardize the subject and may require medical or surgical intervention to prevent one of the outcomes listed previously (designated above by a †).
						
Duration	Record the start and stop dates of the adverse event. If less than 1 day, indicate the appropriate length of time and units						
Action taken	Did the adverse event cause Merck product to be discontinued?						
Relationship to Merck Product	
Did Merck product cause the adverse event? The determination of the likelihood that Merck product caused the adverse event will be provided by an investigator who is a qualified physician. The investigator's signed/dated initials on the source document or worksheet that supports the causality noted on the AE form, ensures that a medically qualified assessment of causality was done. This initialed document must be retained for the required regulatory time frame. The criteria below are intended as reference guidelines to assist the investigator in assessing the likelihood of a relationship between the test drug and the adverse event based upon the available information.
 
The following components are to be used to assess the relationship between Merck product and the AE; the greater the correlation with the components and their respective elements (in number and/or intensity), the more likely Merck product caused the adverse event (AE):
 

Exposure	Is there evidence that the subject was actually exposed to Merck product such as: reliable history, acceptable compliance assessment (pill count, diary, etc.), expected pharmacologic effect, or measurement of drug/metabolite in bodily specimen?	

Time Course	Did the AE follow in a reasonable temporal sequence from administration of Merck product? Is the time of onset of the AE compatible with a drug-induced effect (applies to trials with investigational medicinal product)?	

Likely Cause	Is the AE not reasonably explained by another etiology such as underlying disease, other drug(s)/vaccine(s), or other host or environmental factors	

	Exposure	Is there evidence that the subject was actually exposed to Merck product such as: reliable history, acceptable compliance assessment (pill count, diary, etc.), expected pharmacologic effect, or measurement of drug/metabolite in bodily specimen?	Time Course	Did the AE follow in a reasonable temporal sequence from administration of Merck product? Is the time of onset of the AE compatible with a drug-induced effect (applies to trials with investigational medicinal product)?	Likely Cause	Is the AE not reasonably explained by another etiology such as underlying disease, other drug(s)/vaccine(s), or other host or environmental factors
Exposure	Is there evidence that the subject was actually exposed to Merck product such as: reliable history, acceptable compliance assessment (pill count, diary, etc.), expected pharmacologic effect, or measurement of drug/metabolite in bodily specimen?						
Time Course	Did the AE follow in a reasonable temporal sequence from administration of Merck product? Is the time of onset of the AE compatible with a drug-induced effect (applies to trials with investigational medicinal product)?						
Likely Cause	Is the AE not reasonably explained by another etiology such as underlying disease, other drug(s)/vaccine(s), or other host or environmental factors						

Relationship to Merck Product (continued)		The following components are to be used to assess the relationship between the test drug and the AE: (continued)	
	Dechallenge	
Was Merck product discontinued or dose/exposure/frequency reduced?
 
If yes, did the AE resolve or improve?
 
If yes, this is a positive dechallenge. If no, this is a negative dechallenge.
 
(Note: This criterion is not applicable if: (1) the AE resulted in death or permanent disability; (2) the AE resolved/improved despite continuation of the Sponsor's product; or (3) the trial is a single-dose drug trial); or (4) Sponsor's product(s) is/are only used one time.)
	
	Rechallenge	
Was the subject re-exposed to Merck product in this study?
 
If yes, did the AE recur or worsen?
 
If yes, this is a positive rechallenge. If no, this is a negative rechallenge.
 
(Note: This criterion is not applicable if: (1) the initial AE resulted in death or permanent disability, or (2) the trial is a single-dose drug trial); or (3) Sponsor's product(s) is/are used only one time).
 
NOTE: IF A RECHALLENGE IS PLANNED FOR AN ADVERSE EVENT WHICH WAS SERIOUS AND WHICH MAY HAVE BEEN CAUSED BY MERCK PRODUCT, OR IF REEXPOSURE TO MERCK PRODUCT POSES ADDITIONAL POTENTIAL SIGNIFICANT RISK TO THE SUBJECT, THEN THE RECHALLENGE MUST BE APPROVED IN ADVANCE BY THE SPONSOR AS PER DOSE MODIFICATION GUIDELINES IN THE PROTOCOL.
	
	Consistency with Trial Treatment Profile	Is the clinical/pathological presentation of the AE consistent with previous knowledge regarding Merck product or drug class pharmacology or toxicology?	
The assessment of relationship will be reported on the case report forms /worksheets by an investigator who is a qualified physician according to his/her best clinical judgment, including consideration of the above elements.			
Record one of the following		Use the following scale of criteria as guidance (not all criteria must be present to be indicative of Merck product relationship).	
Yes, there is a reasonable possibility of Merck product relationship.		There is evidence of exposure to Merck product. The temporal sequence of the AE onset relative to the administration of Merck product is reasonable. The AE is more likely explained by Merck product than by another cause.	
No, there is not a reasonable possibility of Merck product relationship		Subject did not receive the Merck product OR temporal sequence of the AE onset relative to administration of Merck product is not reasonable OR the AE is more likely explained by another cause than the Merck product. (Also entered for a subject with overdose without an associated AE.)	

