## **5.6 Rescue Medications & Supportive Care**

### **5.6.1 Supportive Care Guidelines**

Subjects should receive appropriate supportive care measures as deemed necessary by the treating investigator. Suggested supportive care measures for the management of adverse events with potential immunologic etiology are outlined below. Where appropriate, these guidelines include the use of oral or intravenous treatment with corticosteroids as well as additional anti-inflammatory agents if symptoms do not improve with administration of corticosteroids. Note that several courses of steroid tapering may be necessary as symptoms may worsen when the steroid dose is decreased. For each disorder, attempts should be made to rule out other causes such as metastatic disease or bacterial or viral infection, which might require additional supportive care. The treatment guidelines are intended to be applied when the investigator determines the events to be related to pembrolizumab.

Note: if after the evaluation the event is determined not to be related, the investigator does not need to follow the treatment guidance (as outlined below). Refer to Section 5.2.1 for dose modification.

It may be necessary to perform conditional procedures such as bronchoscopy, endoscopy, or skin photography as part of evaluation of the event.

- **Pneumonitis:**

- For **Grade 2 events**, treat with systemic corticosteroids. When symptoms improve to Grade 1 or less, steroid taper should be started and continued over no less than 4 weeks.
- For **Grade 3-4 events**, immediately treat with intravenous steroids. Administer additional anti-inflammatory measures, as needed.
- Add prophylactic antibiotics for opportunistic infections in the case of prolonged steroid administration.
- If grade 2 or higher pneumonitis occurs in patients receiving concurrent radiation therapy to the chest, radiation therapy will be suspended immediately.

- **Diarrhea/Colitis:**

Subjects should be carefully monitored for signs and symptoms of enterocolitis (such as diarrhea, abdominal pain, blood or mucus in stool, with or without fever) and of bowel perforation (such as peritoneal signs and ileus).

- All subjects who experience diarrhea/colitis should be advised to drink liberal quantities of clear fluids. If sufficient oral fluid intake is not feasible, fluid and electrolytes should be substituted via IV infusion. For Grade 2 or higher diarrhea, consider GI consultation and endoscopy to confirm or rule out colitis.

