- b. In subjects who discontinue study therapy without documented disease progression, every effort should be made to continue monitoring their disease status as per the follow-up schedule until (1) the start of new anti-cancer treatment, (2) documented disease progression, (3) death, or (4) the end of the study, whichever occurs first.
- c. In general, the window for each visit is  $\pm$  3 days unless otherwise noted.
- d. Written consent must be obtained prior to performing any protocol specific procedure. Results of a test performed prior to the subject signing consent as part of routine clinical management are acceptable in lieu of a screening test if performed within the specified time frame (e.g., within 28 days prior to the first dose of trial treatment). Screening number will be assigned when the study informed consent is signed.
- e. Prior medications – Record all medications taken within 28 days of screening visit. Concomitant medications – Enter new medications started during the trial through the Safety Follow-up visit. Record all medications taken for SAEs as defined in Section 7.2.
- f. For patients treated for aggressive NHL, cycle#2 of pembrolizumab will occur during EBRT
- g. AEs and laboratory safety measurements will be graded per NCI CTCAE version 4.0. All AEs, will also be evaluated for seriousness. Record all AEs occurring within 30 days after the last dose of trial treatment. Report all SAEs (related and unrelated to trial treatment) and ECIs occurring up until 90 days after the last dose of trial treatment or the start of new anti-cancer treatment, whichever comes first. Afterwards, report only SAEs and ECIs that are related to trial treatment.
- h. Vital signs to include temperature, pulse, respiratory rate, weight and blood pressure. Height will be measured at visit 1 only.
- i. For women of reproductive potential, a urine pregnancy test should be performed within 72 hours prior to first dose of trial treatment. If urine pregnancy results cannot be confirmed as negative, a serum pregnancy test will be required.
- j. Coagulation factors (PT/INR and aPTT) should be tested as part of the screening procedures for all subjects. Any subject receiving anticoagulant therapy should have coagulation factors monitored closely throughout the trial.
- k. After Cycle 1, lab samples can be collected up to 72 hours prior to the scheduled time point. See Section 7.1.3 for details regarding laboratory tests.

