Additionally, any serious adverse event, considered by an investigator who is a qualified physician to be related to Merck product that is brought to the attention of the investigator at any time following consent through the end of the specified safety follow-up period specified in the paragraph above, or at any time outside of the time period specified in the previous paragraph also must be reported immediately to the Sponsor and to Merck Global Safety.

All subjects with serious adverse events must be followed up for outcome.

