#### **8.2 Statistical Analysis Plan**

Phase II design:

The overall response (OR: complete response + partial response) of non-irradiated lesion(s) at three months and dose limiting toxicity (DLT) at one cycles (3 weeks) will be monitored simultaneously using the Bayesian stopping boundaries calculated based on beta-binomial distributions. Independence is assumed between OR and DLT.

DLT is defined as the following toxicities observed during cycle one of the treatment that are considered by the investigator to be related to therapy:

1. Grade 4 neutropenia (ANC < 500/mm3) lasting more than 7 consecutive days.
2. Grade 3 neutropenia with fever and/or infection, where fever is defined as an oral Temperature  $\geq 38.5^{\circ}\text{C}$ .
3. Grade 4 thrombocytopenia (platelets < 25,000/mm3) lasting more than 7 consecutive Days.
4. Grade 3 thrombocytopenia with clinically significant bleeding.
5. A platelet count < 10,000/mm3 at any time.
6. Grade 3 or greater nausea and/or emesis despite the use of optimal anti-emetic Prophylaxis. Optimal anti-emetic prophylaxis is defined as an anti-emetic regimen that employs a 5-HT3 antagonist given in standard doses and according to standard schedules.
7. Grade 3 or greater diarrhea that occurs despite maximal supportive therapy.
8. Any other Grade 3 or greater non-hematologic toxicity with the following exceptions: Grade 3 arthralgia/myalgia or brief (< 1 week) Grade 3 fatigue.
9. A delay of more than 2 weeks in the initiation of Cycle 2 of treatment because of a lack of adequate recovery of therapy related hematological or non-hematologic toxicities.

In cohort 1 for the patients with multiple sites of aggressive NHL, we will consider that the regimen is promising if the OR rate of the non-irradiated lesion (s) at 3 months is at least 35% and the DLT rate at cycle one is below 30%. A sample size of 20 ensures that, if the trial is not terminated early, a posterior 90% credibility interval for OR rate at 3 months will have width of 0.335 at most, when 7 responses are observed out of the 20 patients, under the assumption of 35% OR rate. The prior probability of OR and DLT for the regimen are modeled by beta distribution ( $\text{Beta}(0.35, 0.65)$  and  $\text{Beta}(0.3, 0.7)$ , respectively). Denoting the probability of OR and DLT by  $\{\theta_{\text{OR}}, \theta_{\text{DLT}}\}$ , and they are compared to fixed targets of OR and DLT rates. The following decision criteria will be applied:

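### Adverse-event causality is specified for the Merck product only, although the trial tests pembrolizumab plus EBRT, and two safety passages conflict on events attributed to radiation

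*Combined protocol and SAP*

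**What the plan says.** Table 2 (section 5.2) lists pembrolizumab and EBRT as the trial treatment. Secondary objective 1 (section 3.2) is the safety of the two together.

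Table 6 (section 7.2.3) asks one causality question, "Did Merck product cause the adverse event", answered Yes or No, and one action-taken question, "Did the adverse event cause Merck product to be discontinued". The Yes row describes an event better explained by the Merck product than by anything else. The No row includes "OR the AE is more likely explained by another cause than the Merck product". The table calls these criteria guidance and leaves the answer to the investigator's clinical judgment.

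Four other places depend on attribution:

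- Section 8.2 defines DLTs as listed "toxicities observed during cycle one of the treatment that are considered by the investigator to be related to therapy".
- Section 7.2.2.1 extends SAE reporting beyond the fixed window to any SAE "considered by an investigator who is a qualified physician to be related to Merck product".
- Footnote g of the flow chart (section 6.1) covers the same period differently: "Afterwards, report only SAEs and ECIs that are related to trial treatment".
- Section 5.6.1 says its guidelines are meant for events judged related to pembrolizumab, and adds that "if after the evaluation the event is determined not to be related, the investigator does not need to follow the treatment guidance". Within those guidelines stands "If grade 2 or higher pneumonitis occurs in patients receiving concurrent radiation therapy to the chest, radiation therapy will be suspended immediately". A parallel sentence suspends EBRT for grade 3 or higher diarrhea or colitis when the bowel is being irradiated.

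**The concern.** Lung and bowel toxicity can come from either treatment, and section 5.6.1 anticipates both during concurrent EBRT. A record that asks only about one of the two cannot show which events belong to radiation, to both treatments, or to neither. That weakens the evidence for the combination's safety, and it leaves the DLT standard in section 8.2 without a specified data item behind it. The two conflicts matter in practice as well: sites cannot tell whether a late radiation SAE must be reported, or how the note and the suspension sentences in section 5.6.1 fit together.

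**Working it through.** **1. Does the Merck product include EBRT?** Section 7.2 does extend the term to protocol-specified procedures, but only those made, licensed, provided or distributed by Merck. Table 2 and section 5.2.1.1 describe EBRT as standard of care under institutional practice. EBRT is therefore outside the term.

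**2. What Table 6 records in each case.**

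| Investigator's view of the event | Row whose wording fits | What is recorded about EBRT |
|---|---|---|
| Pembrolizumab more likely | Yes | nothing |
| Radiation more likely | No | nothing |
| Equal or joint cause | neither | nothing |
| Neither treatment | No | nothing |

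The second and fourth cases give the same entry. On this item alone, a radiation toxicity cannot be told from an event unrelated to any trial treatment.

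**3. How often the question arises.** EBRT starts on Day 1 and pembrolizumab on Day 2 (section 2.1). Sections 5.4 and 8.1 give 40-50 Gy in fractions of 3 Gy or less. The minimum is 40 / 3 = 13.3, so 14 fractions. At five per week that spans at least 18 calendar days (two full weeks, then days 15 to 18) of a 21-day cycle. On those figures both treatments run through most of the DLT window. Table 2 still shows a wider dose range; this step uses sections 5.4 and 8.1.

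**4. The DLT rule.** Inputs from section 8.2 are a Beta(0.3, 0.7) prior, 10 patients, and stopping when the posterior probability that the DLT rate exceeds 0.30 is above 0.95. With x DLTs the posterior is Beta(0.3 + x, 0.7 + 10 - x). The probability is 0.890 at x = 5 and 0.969 at x = 6, which reproduces the plan's boundary of 6. The boundary is correct for a given count. Attribution matters only to what enters x. Section 8.2 uses relation to therapy for that, does not refer to Table 6, and does not say whether therapy means pembrolizumab, EBRT or either.

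**5. Late SAEs.** With no new anticancer therapy, both reporting windows close 90 days after treatment.

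| SAE | Section 7.2.2.1 | Footnote g |
|---|---|---|
| Inside the window, any cause | report | report |
| After the window, related to pembrolizumab | report | report |
| After the window, related to EBRT only | not required | report |

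The third row is a direct conflict, because Table 2 makes EBRT a trial treatment.

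**6. Section 5.6.1.** The note releases the investigator from the guidance when an event is judged not related to pembrolizumab. The two suspension sentences are part of that guidance, but they depend on grade and irradiated site and carry no attribution condition. For pneumonitis or colitis attributed to radiation, the note and the sentences point different ways.

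**7. What is not lost.** All AEs to 30 days are reported (section 7.2), and SAEs inside the window are reported whether or not related (section 7.2.2.1). The analysis plans tabulate toxicity by type and severity, not by attribution.

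**The case against.** The strongest reply is that Table 6 compels nothing. Its criteria are guidance, the answer rests on clinical judgment, and Yes means only a reasonable possibility. Section 7.1.2.1 separately asks for causality without limiting it to the Merck product, and the case report form is not among the documents, so it may hold an EBRT item. All of this stands. It means only that the plan does not specify EBRT attribution, which is the point made here.

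Four stronger readings are tempting, and the documents do not support them:

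- *No is mandatory for radiation toxicity.* The guidance status of the rows rules this out.
- *Combined toxicity is filed as unrelated.* The No row needs another cause to be more likely, so joint causation is left unaddressed. A No also means not related to the Merck product; it does not mean unrelated to trial therapy.
- *DLTs are undercounted and the stopping rule loses sensitivity.* This would need the Table 6 answer to decide DLTs. No passage says so, and the wording of section 8.2 already lets radiation or joint toxicity count. The share lost would also be a pure assumption, so no change in stopping probability is claimed.
- *Radiation toxicity falls outside the rule that suspends radiation.* This is one reading of section 5.6.1. The note is permissive and the suspension sentences are specific and imperative, so they can equally be read as standing alone. The passages conflict; the text does not settle which governs.

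**Conclusion.** The concern holds as a gap in attribution and as two internal conflicts. The specified causality and action-taken items cover one of the two trial treatments, so they cannot by themselves support a statement about the safety of the combination. Every AE that the investigator attributes wholly or partly to radiation is affected in its attribution. In collection, the loss is confined to SAEs after the reporting window that relate to EBRT only, which footnote g requires and section 7.2.2.1 does not. The conflict in section 5.6.1 concerns two sentences on suspending EBRT.

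The documents give no number for any of these. A DLT undercount is possible only if sites let the Merck-product answer decide relation to therapy. The conclusion assumes that Table 6 is the full specification of the causality item; an EBRT field on the unseen form would narrow the first part but leave both conflicts. The change should be made: it bears on safety and costs little.

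**What to change.** - In Table 6 and on the AE form, record relationship and action taken separately for pembrolizumab and for EBRT, and allow Yes to both. No third field for the combination is needed, since two Yes answers capture joint causation.
- In section 8.2, state that relation to pembrolizumab, to EBRT or to both meets the DLT standard.
- In section 7.2.2.1, replace relation to the Merck product, for SAEs outside the window, with relation to trial treatment (pembrolizumab and/or EBRT), to match footnote g.
- The sponsor should reconcile the note in section 5.6.1 with the two EBRT-suspension sentences. This review does not say which should govern.

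The cost is one added attribution item per AE with its action-taken counterpart, a few sentences of amended text, and somewhat more events recorded as related.
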